If a flare/relapse is suspected during the treatment period, the Investigator must consult the Contract Research Organization (CRO)-designated Medical Expert to review and harmonize the elements of the diagnostic work-up. Flare/relapse is defined as a re-increase of CRP from normal to 1 mg/dL or greater and/or of ESR from less than 20 mm in the first hour to 30 mm or greater AND at least one of the following signs or symptoms attributed by the Investigator to new, worsening, or recurrent GCA:

- Cranial symptoms
 - New or recurrent headache or pain or tenderness of the scalp or the temporal artery
 - Visual signs/symptoms such as ischemic retinopathy, optic neuropathy, diplopia, amaurosis fugax, etc.
 - New or recurrent claudication of the tongue, masseter muscle, or worsening temporal artery signs and symptoms
 - Transient ischemic attack (TIA) or stroke related to GCA in the opinion of the Investigator
- Extracranial symptoms
 - Classic PMR-like symptoms, defined as shoulder and/or hip girdle pain associated with inflammatory morning stiffness
 - New or recurrent claudication in the peripheral circulation (i.e., in one of the extremities)
- New or worsening angiographic abnormalities detected via MRI, CT/CTA, or PET-CT of the aorta or other great vessels or via ultrasound of the temporal arteries

Supportive findings could include other symptoms in the opinion of the Investigator related to worsening GCA, such as sustained daily recurrent fever with a temperature over 38°C for more than 1 week, chronic anemia, or unexplained weight loss.

Although either acute phase reactant (CRP or ESR) may be used during the study for eligibility and to determine remission or flares, it is advisable that the same acute phase reactant used to determine remission at screening also be used to determine flares during the treatment period.

All elements of the diagnostic work-up pertinent to the Investigator diagnosis of a flare/relapse (i.e., the primary efficacy endpoint) should be reviewed with the CRO-designated Medical Expert and entered into the electronic Case Report Form (eCRF) promptly.

Flare/relapse is defined as major if cranial symptoms or ischemia-related visual loss are present or if there is clear evidence of new onset large vessel vasculitis (e.g., subclavian artery). In all other situations, flare/relapse attributed to PMR, vascular or other symptoms should be regarded as minor.

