- c) AND at least one of the following:

- i. TAB or ultrasound revealing features of GCA
- ii. Evidence of large-vessel vasculitis by angiography or cross-sectional imaging study such as MRI, CT/CTA, or PET-CT of the aorta or other great vessels

Relapsing: Diagnosis of GCA > 6 weeks before Day 0 AND:

Active GCA within 6 weeks of Day 0 defined as clinical sign/symptom(s) as per above and Westergren ESR > 30 mm/hour or CRP \geq 1 mg/ dL

Refractory nonremitting: Diagnosis of GCA > 6 weeks before Day 0 AND:

No remission since the diagnosis of disease as per clinical expectations. i.e. Presence of sign/symptoms as per above and Westergren ESR > 30 mm/hour or CRP \geq 1 mg/ dL within 6 weeks of Day 0.

4. Remission of GCA at or before Day 0 (resolution of GCA symptom(s) and CRP < 1.0 mg/dL or ESR < 20 mm in the first hour), such that the subject can safely participate in the study and follow the protocol-defined procedures, including initiation of the prednisone taper at the protocol-specified starting dose (i.e., \leq 60 mg/day)
5. At Day 0, receiving or able to receive oral prednisone up to 60 mg/day for the treatment of GCA
6. If using methotrexate (MTX), oral or parenteral up to 25mg/week is permitted in screening if started more than 6 weeks prior to Day 0 and should be tapered to zero by Day 0
7. Willing to receive antiplatelet therapy depending on the Investigator's decision
8. Willing to receive treatment for prevention of corticosteroid-induced osteopenia/osteoporosis depending on the Investigator's decision
9. Female subjects must be:
 - a) postmenopausal, defined as at least 12 months post cessation of menses (without an alternative medical cause), or
 - b) permanently sterile following documented hysterectomy, bilateral salpingectomy, bilateral oophorectomy, or tubal ligation or having a male partner with vasectomy as affirmed by the subject, or
 - c) nonpregnant, nonlactating, and if sexually active having agreed to use a highly effective method of contraception (i.e., hormonal contraceptives associated with inhibition of ovulation or intrauterine device [IUD], or intrauterine hormone-releasing system [IUS], or sexual abstinence) from Screening Visit until the Final Washout Safety Follow-up visit 84 ± 3 days from EOT Visit.

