 - The refractory nonremitting disease subject has no remission since the diagnosis of disease as per clinical expectations. Thus, the subject has documentation of prior diagnosis of GCA as per above Diagnostic Criteria > 6 weeks before Day 0; however, presence of Acute Phase Reactants and Signs/Symptoms as per above persists within 6 weeks of Day 0.

Subjects who complete screening procedures and are not considered eligible (screen failures) may be rescreened one time provided there is reason to believe that eligibility criteria will be met.

Stratified eligible subjects will enter the double-blind treatment period after randomization 3:2 to blinded treatment with KPL-301 150 mg or placebo administered SC every other week (every 2 weeks). All subjects will also receive an unblinded 26-week oral prednisone taper according to a standardized tapering protocol.

Prior to first administration of KPL-301 or placebo, all subjects are required to achieve remission (i.e., resolution of GCA symptom(s) and CRP < 1.0 mg/dL or ESR < 20 mm in the first hour). Should a subject in screening not achieve remission by > 6 weeks of onset they can be rescreened using their prior flare documentation following the relapsing/refractory non-remitting inclusion criteria.

The first administration of subcutaneous KPL-301/placebo and oral prednisone taper will take place at the study site on Day 0. Subsequent doses of KPL-301/placebo will be administered at the study site in conjunction with a scheduled study visit or administered by the subject on an outpatient basis in accordance to the dosing schedule. The oral steroid taper will be self-administered by study subjects on a daily basis.

Subjects will be followed at the study site at Weeks 1, 2, 3, 4, and approximately every 4 weeks thereafter (see Table 1). Subjects reporting worsening of GCA symptoms or any safety issues may be brought in for an unscheduled visit at the study site at any time.

If a flare/relapse is suspected, the Investigator must consult the Contract Research Organization (CRO)-designated Medical Expert to review and harmonize the elements of the diagnostic work-up.

Flare/relapse is defined as a re-increase of CRP from normal to 1 mg/dL or greater and/or of ESR from less than 20 mm in the first hour to 30 mm or greater AND at least one of the following signs or symptoms attributed by the Investigator to new, worsening, or recurrent GCA:

- Cranial symptoms

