### **6.7. Efficacy Analysis**

All efficacy analyses will be conducted by treatment for the mITT analysis set. Selected analyses may be in the PP analysis set. Endpoints involving flare will be based on adjudication primarily. Investigator assessment will only be used supportively.

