### 6.7.2. Analysis of Primary Efficacy Endpoint

The primary endpoint of time to flare by Week 26, is defined as time from randomization to the first flare occurring within the treatment period. Flare/relapse is defined as a C-reactive protein (CRP) of 1 mg/dL or greater and/or erythrocyte sedimentation rate (ESR) of 30 mm/h or greater AND at least one of the following signs or symptoms attributed to GCA:

- Cranial symptoms
  - New-onset localized headache
  - Scalp or temporal artery tenderness
  - Ischemic-related vision loss
  - Unexplained mouth or jaw pain upon mastication (i.e. claudication of tongue)
  - Transient ischemic aattach or stroke related to GCA
- Extracranial symptoms
  - Claudication of the extremities
  - Symptoms of PMR (shoulder & hip girdle pain associated with inflammatory morning stiffness)
- New or worsening angiographic abnormalities detected via MRI, CT/CTA, or PET-CT of the aorta or other great vessels or via ultrasound of the temporal arteries.

Supportive findings could include other symptoms related to worsening GCA, such as sustained daily recurrent fever with a temperature over 38°C for more than 1 week, chronic anemia, or unexplained weight loss.

Subjects who do not experience a flare during this period will be censored according to [Table 1](#) End of treatment (EOT) in the table refers to early discontinuation of treatment.

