**Table 1: Censoring Rules for Time to Flare by Week 26**

	Scenario	Event or Censoring	Censoring Reason	Date of Event or Censoring
1	Flare occurrence on or prior to week 26	Event	No censoring	Date of flare
2	No flare occurrence on or prior to week 26	Censored	No flare occurrence	Date of last assessment by week 26
3	No flare occurrence on or prior to EOT	Censored	No flare occurrence by EOT	Date of last assessment by EOT
4	No post baseline assessment	Censored	No assessment	Date of randomization

Time to flare by week 26 will be summarized by the 25th, 50th (median), and 75th percentiles calculated using the Kaplan-Meier (KM) method to estimate the survival functions for each treatment group. The 95% confidence interval (CI) for the percentiles will be calculated using a log-log transformation. Plots of survival curves by treatment using the KM method will be presented. Additional survival plots will be provided by treatment for the stratification factor.

A log-rank test stratified by the stratification factor (disease status) will be used as the primary treatment comparison between KPL-301 and placebo. To describe the magnitude of treatment effect, the hazard ratio for KPL-301 compared to placebo and the corresponding Wald 95% CI will be

calculated based on a Cox proportional-hazards model with treatment as a covariate and stratified by the stratification factor.

If subjects were randomized based on incorrect stratum, then the corrected stratum will be used for stratified analyses rather than the incorrect stratum recorded at randomization.

The primary analysis of time to flare will be based on the adjudication outcome. Time to flare per investigator's assessment will be used as a supportive analysis of the primary endpoint. A 2x2 table of concordance will be used to assess the agreement between adjudicated and investigator assessments.

As a sensitivity analysis, the stratified analyses of time to flare based on adjudication will be repeated for the per protocol analysis set defined in Section 2.3 .

The stratified analyses of time to flare based on adjudication will also be repeated for the mITT analysis set by censoring subjects without flare before EOT at the last assessment date by week 26. That is, the censoring does not take into consideration of the early treatment discontinuation. The scenario 3 in the censoring table follows scenario 2 rule.

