#### **6.7.3.3. *Time to elevated CRP by week 26***

Time to elevated CRP will be defined as the time from randomization to earliest date of a CRP value of  $\geq 1.0$  mg/dL. All subjects who do not have an elevated CRP by week 26/ EOT will be censored at last assessment date or the randomization date, whichever is later. Detailed censoring rule follows that for ESR. Subjects with elevated CRP at baseline will be excluded from the analysis.

Analysis and presentation will be the same as that of the primary efficacy endpoint. The KM method to estimate the survival functions for each treatment group (overall and by stratification factor). The treatment comparison will be based on a stratified log-rank test. The HR and its 95% CI will be estimated using a stratified Cox model with treatment as the explanatory variable and strata as the stratification factor.

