**6.7.3.7. *Percentage of subjects who have completed the corticosteroid taper and who have a normal CRP by week 26***

[figure not shown]
The number and percentage of subjects who complete the corticosteroid taper and have normal C-reactive protein (<1.0 mg/dL) by week 26 will be presented by treatment. Having normal CRP by week 26 requires all assessments of CRP from the completion of corticosteroid taper through week 26 being normal. If there is no assessment after completion of taper, the subject will not be counted in the numerator.

[figure not shown]
[figure not shown]
[figure not shown]
[figure not shown]
The percentage will be compared between the treatment groups using a Cochran-Mantel-Haenszel test controlling for the stratification factor; the 95% confidence interval for the difference of percentages will be displayed using the Mantel-Haenszel weight for the stratification factor.

[figure not shown]
[figure not shown]
**6.7.3.8. *Percentage of subjects who completed the corticosteroid taper and who have no signs/symptoms of GCA or new or worsening vasculitis by imaging by week 26***

The number and percentage of subjects who complete the corticosteroid taper and who have no signs/symptoms of GCA by week 26 will be presented by treatment. Having no signs/symptoms of GCA by week 26 requires all assessments of from the completion of corticosteroid taper through week 26 showing no signs/symptoms of GCA or new or worsening vasculitis by imaging by week 26. If there is no assessment after completion of taper, the subject will not be counted in the numerator.

The percentage will be compared between the treatment groups using a Cochran-Mantel-Haenszel test controlling for the stratification factor; the 95% confidence interval for the difference of percentages will be displayed using the Mantel-Haenszel weight for the stratification factor.

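### SAP 6.7.2 defines the laboratory half of the primary flare event by absolute CRP or ESR level, the protocol requires a re-increase, and the SAP does not list the change

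*SAP*

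**What the plan says.** The Protocol Synopsis (Base Treatment Period) sets a starting level for each marker: "Flare/relapse is defined as a re-increase of CRP from normal to 1 mg/dL or greater and/or of ESR from less than 20 mm". Section 8.4.1 repeats it, with the ESR limb running as "ESR from less than 20 mm in the first hour to 30 mm or greater". Both add that a sign, symptom or imaging finding attributed to GCA must be present.

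SAP 6.7.2 keeps the clinical half in abbreviated form but gives the laboratory half as a level only: "Flare/relapse is defined as a C-reactive protein (CRP) of 1 mg/dL or greater and/or erythrocyte sedimentation rate (ESR) of 30 mm/h or greater". No starting value is mentioned.

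Inclusion criterion 4 (Synopsis and 8.7.1) sets entry as "Remission of GCA at or before Day 0 (resolution of GCA symptom(s) and CRP < 1.0 mg/dL or ESR < 20 mm". One controlled marker is enough, and it may have been measured before Day 0.

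The SAP has one rule on a raised baseline marker. It belongs to a secondary endpoint, time to elevated CRP (6.7.3.3): "Subjects with elevated CRP at baseline will be excluded from the analysis". The Synopsis recommends, without requiring, that the marker used to establish remission at screening also be used to judge flare. The SAP does not take this up.

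SAP 6.7 states: "Endpoints involving flare will be based on adjudication primarily". For the investigator comparison, SAP 6.7.2 adds: "A 2x2 table of concordance will be used to assess the agreement between adjudicated and investigator assessments". SAP 7.1 lists six changes from the protocol. Two concern flare, and both are about symptom categories.

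**The concern.** If every subject entered with both markers normal, the two wordings would nearly coincide. The entry rule does not ensure that. A subject can qualify on one marker while the other is raised, and so meet the SAP's laboratory half from the first day. A later GCA-attributed finding would then complete a flare under the SAP with no re-increase.

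The trial is planned on about 20 events, so a few reclassified subjects could matter. The primary test also comes first in the testing order of SAP 6.7.1, and the first secondary endpoint, sustained remission, uses the same adjudicated flare. If the conflict is still open at unblinding, someone must choose between two written definitions with the results in view.

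**Working it through.** **1. The plan's own figures reproduce.** Inputs from SAP 1.3 and Protocol 14.2 and 8.6: flare-free at Week 26 is 50% on placebo and 85% on KPL-301; 42 and 28 subjects; two-sided 0.05.

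- HR = ln(0.85)/ln(0.50) = 0.2345 (stated 0.234).
- Expected events = 28 × 0.50 + 42 × 0.15 = 14 + 6.3 = 20.3 (stated about 20).
- Power at 20 events, Freedman formula with k = 1.5: √(20 × 1.5) × (1 − 0.2345)/(1 + 1.5 × 0.2345) − 1.96 = 1.14, giving 87.3% (stated 87%).

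The sample size is not in error.

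**2. Eligible subjects on whom the definitions differ.** Each also has a GCA-attributed finding.

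| Baseline | Later | Protocol laboratory half | SAP laboratory half |
|---|---|---|---|
| CRP below 1.0, ESR 35 | CRP still below 1.0, ESR 35 | Not met | Met |
| CRP below 1.0, ESR 25 | CRP still below 1.0, ESR 35, never below 20 | Not met | Met |
| ESR 15, CRP 1.5 | ESR still 15, CRP 1.5 | Not met | Met |

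**3. What the protocol's normal CRP means is also unsettled.** The flare text gives no number. The remission criterion uses below 1.0 mg/dL, and SAP 6.7.3.7 calls that level normal ("have normal C-reactive protein (<1.0 mg/dL) by week 26"). Protocol 12.2.4 refers to normal values of 0.5 mg/dL or less.

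**4. Illustration of size.** The documents do not say how many subjects start with a raised marker, so every rate here is assumed. Let f be the share with a raised marker at baseline. Let q be the placebo probability, among these, of a GCA-attributed finding by Week 26 without re-increase. Let h be the drug's hazard ratio on such findings, so that on KPL-301 q₁ = 1 − (1 − q)^h. Take f and q from 10% to 30%.

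Added events = 28 × 0.50 × f × q + 42 × 0.85 × f × q₁. Resulting HR = ln[0.85(1 − f q₁)]/ln[0.50(1 − f q)].

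At f = q = 30%:

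| h | q₁ | Added events (placebo + KPL-301) | HR | Simulated power |
|---|---|---|---|---|
| 1 (no drug effect) | 0.300 | 1.26 + 3.21 = 4.47 | 0.326 | about 80% |
| 0.5 | 0.163 | 1.26 + 1.75 = 3.01 | 0.270 | about 88% |
| 0.234 | 0.080 | 1.26 + 0.86 = 2.12 | 0.237 | about 92% |

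Power is from simulation: 42 versus 28 subjects, two equal strata, exponential times, 26 weeks, stratified log-rank. On the same basis the unmodified design has about 90%. At f = q = 10% with h = 1, added events are 49.7 × 0.01 = 0.50, HR is 0.245 and power about 89%. With a drug effect it stays at about 90% or slightly above.

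With h = 1 the two definitions give different verdicts in about 2% to 12% of simulated trials; with h = 0.234, in about 1% to 5%. With no treatment effect at all, two-sided rejection is 5.0% to 5.3% under both definitions.

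**The case against.** The strongest reply is that the primary event is an adjudicator's verdict, not a derivation from SAP 6.7.2. Adjudicators may be working to the protocol text, and a case meeting only the SAP wording must first be suspected, referred and judged positive. This stands as a limit on size. It does not settle the matter: neither document gives the adjudication criteria, and 6.7.2 holds the SAP's only flare definition. The investigator-based analysis and the concordance table help in part, but cannot separate a different definition from a different judgement.

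The second reply is that the protocol already deals with this subject through the same-marker recommendation. If followed, the marker still raised would not be the one used to judge flare. But the recommendation is not binding, appears only in the Synopsis and is absent from the SAP. It also does not help the subject whose qualifying marker is no longer controlled by baseline, since remission may predate Day 0. The supportable statement is that no binding rule exists, not that the documents are silent.

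Third, a reader might infer from the h = 1 row that the SAP wording costs ten points of power. The documents do not support that. That row assumes the drug does nothing to GCA-attributed findings while cutting flares by three quarters. Give it the planned effect on both and power does not fall. The added-event count is also one-sided, because the abbreviated symptom categories, which SAP 7.1 does disclose, could remove events if read literally.

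**Conclusion.** The point holds as a contradiction in the definition of the primary event, and it rests on the texts alone. The protocol requires starting levels, the SAP drops them, SAP 7.1 does not say so, and the entry rule admits subjects on whom the two definitions disagree.

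The consequence cannot be sized, and its direction is not determined. It depends on how many subjects start with a marker that is not normal, on the drug's effect on later findings in those subjects, and on the adjudication criteria. The documents give none of these. The illustration shows only that the effect could range from negligible to about ten points of power.

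Two stronger readings should be set aside. A raised marker alone is not a flare under the SAP, because a GCA-attributed finding and a positive adjudication are still needed. Nor does the SAP wording inflate false positives in the cases modelled.

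It should be fixed before unblinding. It does not invalidate the design.

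**What to change.** Before unblinding:

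1. Reconcile SAP 6.7.2 with the protocol's flare definition for the analysis. The default is to restore the starting levels in 6.7.2. Otherwise list and justify the change in SAP 7.1.
2. State how a marker that is not normal at baseline counts for the primary endpoint. Have the sponsor reconcile which normal CRP applies: below 1.0 mg/dL (criterion 4, SAP 6.7.3.7) or 0.5 mg/dL or less (Protocol 12.2.4).
3. Cite in SAP 6.7.2 the document that holds the adjudication criteria, and confirm that it uses the same definition.
4. Prespecify a sensitivity analysis under the other laboratory definition, applied either to the adjudicated cases or as a programmed endpoint from the collected CRP, ESR and symptom data. State whether local or central CRP is used: Protocol Table 1 bases flare decisions on local values but schedules local CRP only at Screening, Day 0 and unscheduled visits, whereas central CRP is taken at every visit.
5. Report, blinded, how many subjects have baseline CRP of 1.0 mg/dL or more, ESR of 20 to 29, and ESR of 30 or more.

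The cost is SAP wording, one reference and a little programming. Baseline CRP and ESR are already defined (SAP 5.1.3) and summarised (SAP 6.3). Cases never referred for adjudication cannot be recovered, so the sensitivity analysis will be incomplete in that respect. Treatment and stopping rules are not affected.

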**Table 1: Censoring Rules for Time to Flare by Week 26**

	Scenario	Event or Censoring	Censoring Reason	Date of Event or Censoring
1	Flare occurrence on or prior to week 26	Event	No censoring	Date of flare
2	No flare occurrence on or prior to week 26	Censored	No flare occurrence	Date of last assessment by week 26
3	No flare occurrence on or prior to EOT	Censored	No flare occurrence by EOT	Date of last assessment by EOT
4	No post baseline assessment	Censored	No assessment	Date of randomization

Time to flare by week 26 will be summarized by the 25th, 50th (median), and 75th percentiles calculated using the Kaplan-Meier (KM) method to estimate the survival functions for each treatment group. The 95% confidence interval (CI) for the percentiles will be calculated using a log-log transformation. Plots of survival curves by treatment using the KM method will be presented. Additional survival plots will be provided by treatment for the stratification factor.

A log-rank test stratified by the stratification factor (disease status) will be used as the primary treatment comparison between KPL-301 and placebo. To describe the magnitude of treatment effect, the hazard ratio for KPL-301 compared to placebo and the corresponding Wald 95% CI will be

calculated based on a Cox proportional-hazards model with treatment as a covariate and stratified by the stratification factor.

If subjects were randomized based on incorrect stratum, then the corrected stratum will be used for stratified analyses rather than the incorrect stratum recorded at randomization.

The primary analysis of time to flare will be based on the adjudication outcome. Time to flare per investigator's assessment will be used as a supportive analysis of the primary endpoint. A 2x2 table of concordance will be used to assess the agreement between adjudicated and investigator assessments.

As a sensitivity analysis, the stratified analyses of time to flare based on adjudication will be repeated for the per protocol analysis set defined in Section 2.3 .

The stratified analyses of time to flare based on adjudication will also be repeated for the mITT analysis set by censoring subjects without flare before EOT at the last assessment date by week 26. That is, the censoring does not take into consideration of the early treatment discontinuation. The scenario 3 in the censoring table follows scenario 2 rule.

Subgroup analyses of the primary efficacy endpoint may be performed with age group, sex, race, and stratification factor.

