### **5.1.7. Week 26**

Week 26 in this document refers to the completion of the treatment period, which might not be exactly the 26th week, e.g. if due to treatment delay/use of + 3 days of out of window visit allowance more than 2 times. Efficacy assessments before the safety follow up will all be included in “at week 26”, or “by week 26” analyses unless otherwise specified.

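### SAP Table 1 gives two answers for a flare after a non-flare drug stop: an event under row 1, censored at EOT under row 3, with no precedence stated

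*SAP*

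**What the plan says.** SAP 6.7.2 defines the primary endpoint, which "is defined as time from randomization to the first flare occurring within the treatment period". Table 1 then sets the rules:

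- Row 1: "Flare occurrence on or prior to week 26" is an event on the flare date.
- Row 2: no flare by Week 26 is censored at the last assessment by Week 26.
- Row 3: "No flare occurrence on or prior to EOT" is censored at the last assessment by EOT.

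A note adds: "End of treatment (EOT) in the table refers to early discontinuation of treatment".

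SAP 5.1.7 states: "Week 26 in this document refers to the completion of the treatment period". It continues: "Efficacy assessments before the safety follow up will all be included in" analyses at or by Week 26, unless something else is specified.

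A sensitivity run on the mITT set takes subjects with no flare before EOT and censors them at the last assessment by Week 26. The SAP explains: "That is, the censoring does not take into consideration of the early treatment discontinuation" and "The scenario 3 in the censoring table follows scenario 2 rule".

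Protocol Table 1 (EOT footnote) keeps early stoppers on their remaining scheduled visits. The synopsis and 8.4.1 give the reason as informative censoring.

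SAP 6.7.3.1 takes the sustained remission rate, first in the secondary hierarchy, from the same Kaplan-Meier curve. SAP Table 2 (time to elevated ESR) repeats the row structure. CRP (6.7.3.3) and signs/symptoms (6.7.3.4) follow the ESR rule.

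**The concern.** Take a subject who stops study drug in week 8 for a reason other than flare, stays on the visit schedule, and has an adjudicated flare in week 18. Row 1 applies because the flare is before Week 26. Row 3 applies because there was no flare by EOT. The protocol's follow-up is designed to observe such flares, so the case is not hypothetical.

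Three things are at stake. The primary event count depends on who programs it. One of the possible combinations of rows gives a biased remission curve. And the run meant to show what happens when the drug stop is ignored does not say that a post-EOT flare becomes an event in it.

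**Working it through.** **1. Text on each side.**

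*For ending at EOT:* the endpoint is limited to the treatment period, which can mean the subject's own time on drug. The censoring sentences for ESR, CRP and signs/symptoms pair Week 26 with EOT as alternatives. The sensitivity run is described as the one that ignores discontinuation, so the primary analysis presumably does not.

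*For running to Week 26:* row 1 names Week 26, not EOT, and SAP 5.1.7 takes in all efficacy assessments before the safety follow-up. That sentence yields to anything specified elsewhere, and row 3 may be such a specification.

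This leaves three readings: (A) everyone ends at EOT; (B) everyone runs to Week 26; (C) mixed, with row 1 taking post-EOT flares and row 3 censoring non-flaring stoppers at EOT.

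**2. Planning figures reproduced** (SAP 1.3; arm sizes from the protocol synopsis). HR = ln 0.85 / ln 0.50 = 0.2345. With 20 events and 3:2 allocation, Freedman's formula gives z = √(20 × 1.5) × (1 − 0.2345)/(1 + 1.5 × 0.2345) − 1.96 = 1.14, or 87% power, as stated. Expected events with 42 v 28 subjects: 42 × 0.15 + 28 × 0.50 = 20.3.

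**3. Direction under C.** Compared with B, the events and their times are identical, but non-flaring stoppers leave the risk set early. Risk sets are never larger, so the curve cannot be higher in any dataset.

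**4. Size under C.** Assume exponential flares (hazard λ) and independent exponential stops (hazard μ), equal in both arms, with flare risk unchanged after the stop. Put T = 26 weeks and let d be the assumed stop proportion, so μT = −ln(1 − d). The risk set at t is e^(−λt) − (1 − e^(−μt))e^(−λT), and the Kaplan-Meier limit is

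exp{ −∫₀ᵀ λe^(−λt) / [e^(−λt) − (1 − e^(−μt))e^(−λT)] dt }.

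| Assumed stops | KPL-301 (truth 85%) | Placebo (truth 50%) |
|---|---|---|
| 5% | 84.7% | 49.3% |
| 10% | 84.3% | 48.5% |
| 25% | 83.0% | 45.9% |
| 40% | 81.2% | 42.5% |

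Trial-size simulations (42 v 28, 6,000 runs) agree: 84.2/48.6, 83.0/45.8 and 81.2/42.7 at 10%, 25% and 40%.

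**5. Readings A and B.** Under the same assumptions both recover 85/50. They differ in events. On-drug flares per subject are q = λ/(λ + μ) × (1 − e^(−(λ+μ)T)). At 25% stops, q = 0.1309 (KPL-301) and 0.4417 (placebo), so A has 42 × 0.1309 + 28 × 0.4417 = 17.9 events against 20.3 under B, a difference of 2.4. At 10% stops the difference is 20.3 − 19.4 = 0.9. Simulated power at 25% stops is 86% (A) and 91% (B). If KPL-301 risk instead returns to the placebo level after the stop, A gives 85/50 with 86% power and B gives 80/50 with 78%.

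**6. Test error under C** (null, 50% flare-free in both arms, stratified log-rank, 6,000 runs). With 25% stops in each arm, the two-sided error is about 5%. With stops of 10% (KPL-301) v 25% (placebo), the total stays near 5% but splits into about 4% favouring KPL-301 and 1.4% favouring placebo. With 25% v 10% it reverses: about 1.7–1.9% and 3.2–3.8%.

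**7. The EOT-ignored run taken at its word.** A subject who flares after EOT has no flare before EOT, so is censored at the last assessment by Week 26. Remission becomes 1 − q. At 10% stops: 1 − 0.1426 = 85.7% and 1 − 0.4774 = 52.3%. At 25%: 86.9% and 55.8%. The bias is upward.

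**The case against.** The strongest reply is that the intended rule is clear enough: the treatment-period wording, the Week 26/EOT pairing and the contrast with the sensitivity run all indicate that the primary analysis ends at EOT. That is the better reading. It still requires overriding row 1, which says Week 26, and the SAP does not say to do so.

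A reader might infer that the table, as written, produces the downward bias. The documents do not support that. Both rows apply to the disputed subject, and the bias needs row 1 to beat row 3 for flarers while row 3 beats row 2 for non-flaring stoppers. Applying the rows top-down gives reading B; letting the specific row govern gives reading A.

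It is also fair that the effect is modest. At 10% stops under one event is in dispute, and the bias is small beside a placebo standard error of about √(0.5 × 0.5/28) = 9 points. That limits the harm but does not justify leaving the rule open when about 20 events are planned. The sensitivity run cannot fill the gap, because it changes only the censoring date.

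**Conclusion.** The overlap is real and should be fixed before unblinding. It affects the primary endpoint and the sustained remission rate, and through Table 2 the ESR, CRP and signs/symptoms endpoints.

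The bias is conditional on the mixed reading: about 1 point or less in KPL-301 and 1.5 points in placebo at an assumed 10% stops, and about 2 and 4 points at 25%. Stop rates are not in the documents, so every size here is an illustration. The absence of bias under the two single-end readings also rests on assumptions: stops unrelated to flare, and unchanged risk afterwards.

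Two opposite inferences about the test should be avoided. Overall type I error inflation is not shown, since the two-sided log-rank error stays near 5%. Nor is the test unaffected: under the mixed reading the two tails become unbalanced when stop rates differ by arm, and the direction depends on which arm stops more.

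**What to change.** Make rows 1 and 3 exclusive, with one end of follow-up for flarers and non-flarers. The text leans towards EOT for the primary analysis, so:

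- Row 1: adjudicated flare on or before the earlier of EOT and Week 26.
- Row 3: stopped early with no flare on or before EOT; a later flare is not an event in this analysis.
- Define the EOT date so that a flare which triggers the stop is included.
- In the EOT-ignored run, add that adjudicated flares after EOT and by Week 26 are events.
- Use the corresponding wording in Table 2, which CRP and signs/symptoms inherit.

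The cost is two rows in each table, an EOT date definition and one sentence, with no new data. Ending at EOT drops post-stop flares from the primary analysis (about 2.4 of 20.3 events at an assumed 25% stops); the corrected EOT-ignored run retains them. If the sponsor prefers Week 26 as the single end, that also removes the overlap, but it mixes off-drug flare risk into the primary comparison.
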